6.2.4. Infant and Child Deaths

This study will assess the proportion of infant and child deaths that occur after 28 days post EDD and up to 24 months chronological age.

6.2.5. Parent/Legal Guardian-Completed ASQ-3, M-CHAT-R/F, and CBCL/1.5–5 and Possible Referral to a Specialist

The parent/legal guardian will be asked to complete standardized developmental screening of the infant through completion of the ASQ-3. The ASQ-3 was developed and validated to be used as a developmental screening tool; it has been used globally and translated into a number of different languages. The tool has been demonstrated to reliably and accurately identify children with delays who should receive further in-depth assessment. The ASQ-3 includes a series of questions designed to assess 5 areas of development: communication, gross motor, fine motor, problem-solving, and personal-social. The questions target behaviors that are appropriate for particular developmental milestones; there are individual ASQ-3 questionnaires for age intervals ranging from 2 to 66 months. These behaviors are easy for parents to observe, and they are asked to indicate whether or not the child can perform the behavior.

The 9-, 18-, and 24-month ASQ-3 questionnaires will be used in this study. These time points comply with recommended developmental screening assessment guidelines from the American Academy of Pediatrics [[Council on Children with Disabilities](#), 2006]. The parent/legal guardian will be asked to complete the 9-, 18-, and 24-month ASQ-3 when the infant's corrected age corresponds to 9, 18, and 24 months, for example, parents/legal guardians of an infant born 3 months premature will complete the 9-month ASQ-3 at 12 months chronological age. To facilitate data collection, the parent/legal guardian will be provided with an electronic device that will enable them to provide the protocol-required data. They will have the option to use alternative ways to access the same system (e.g., their own personal devices). Further details will be provided in the SPM. The completion window for the ASQ-3 is +30 days at Month 9 and ± 30 days at Months 18 and 24; however, questionnaires completed outside the completion window will not be considered a protocol deviation. It is essential to make age adjustments for prematurity when selecting the appropriate ASQ-3. Based on results from the ASQ-3 administered at 24 months corrected age and if no cerebral palsy diagnosis has been made to date (see Section [6.2.5.1](#)), the infant may be referred to a qualified examiner for a formal assessment of cerebral palsy.

The M-CHAT-R/F will be completed for all infants at 18 and 24 months (corrected age) and the CBCL/1.5–5 will be completed for all infants at 24 months (corrected age) to assess the risk for other behavioral problems or ASD. If at any of these time points a child has an M-CHAT-R/F score that indicates further evaluation is required and/or a CBCL/1.5–5 score above the 97th percentile for a subset of prespecified questions, the child will be referred to a specialist for a formal assessment. An overview for the collection and review of data for the M-CHAT-R/F and CBCL/1.5–5 is provided in [Figure 3](#).

The M-CHAT-R/F is a parent-reported autism screening tool designed to identify children 16 to 30 months of age who should receive a more thorough assessment for possible early signs of ASD or developmental delay [Robins, 2014]. The M-CHAT-R/F consists of 20 questions that are answered with either “yes” or “no.” Total scores on the M-CHAT-R/F between 0 and 2 indicate a low risk, scores between 3 and 7 indicate a medium risk and triggers administration of the follow-up questionnaire, and scores between 8 and 20 indicate a high risk. In this study, infants with test scores that indicate that further evaluation is required (either after an initial medium-risk score and further follow-up or an initial high-risk score) will be considered to have possible signs of ASD or developmental delay and will be referred to a developmental specialist for a formal assessment.

The CBCL/1.5–5 is a widely used parent-completed questionnaire of the Achenbach System of Empirically Based Assessment (ASEBA). The ASEBA is based on carefully conducted empirical studies and is designed to assess, in a standardized format, behavioral problems and social competencies (Achenbach, 2001). The CBCL/1.5-5 includes approximately 100 items that describe specific kinds of behavioral, emotional, and social problems that characterize preschool children between the ages of 1.5 and 5 years. Scores on the full CBCL/1.5-5 between the 93rd and 97th percentile are in the borderline range and scores above the 97th percentile are in the significant range of clinical concern. In this study, infants with test scores above the 97th percentile for a subset of prespecified questions that relate to attention or hyperactivity problems syndrome or the American Psychiatric Association's Diagnostic and Statistical Manual (DSM)-oriented attention-deficit/hyperactivity disorder scale will be considered to have a behavior problem, which will trigger a referral to a developmental specialist for a formal assessment.

The completion window for the CBCL/1/5-5 and M-CHAT-R/F is +6 weeks at 18 months (M-CHAT-R/F only) and +12 weeks at 24 months; however, questionnaires completed outside the completion window will not be considered a protocol deviation.

For further details regarding the CBCL/1.5–5 and M-CHAT-R/F, refer to the SPM.

6.2.5.1. The ASQ-3 Score Interpretation and Possible Specialist Referral Recommendations

The ASQ-3 scores for this study will be interpreted and recommendations will be offered according to the following:

[figure not shown]
- The child’s development will be considered to be on schedule if the child’s ASQ-3 scores are in the white zone (higher than 1 SD below the mean), and no further action is required.
- If the child’s ASQ-3 scores are in the grey zone (≤ 1 SD below the mean), the parent/legal guardian may share the ASQ-3 test results with the child’s HCP.

- If any of the child's ASQ-3 scores are in the black zone (≥ 2 SD below the mean), then the child's parent/legal guardian will be asked if the child is already under the care of a developmental specialist who can or has made a formal assessment (e.g., using the BSID-III). If a recent (≤ 3 months) BSID-III was conducted, the BSID-III will not be repeated and the RCC-PI will request results from the relevant HCP. If the child is not currently under the care of a developmental specialist, then the parent/legal guardian will be referred to a qualified assessor for developmental evaluation (e.g., using the BSID-III), and a neurologic examination will be conducted, if indicated.
- BSID-III retesting will be performed if the child's ASQ-3 scores are in the black zone on a subsequent ASQ-3 test following the first BSID-III referral.
- If, at 24 months corrected age, the child's ASQ-3 gross motor domain score is in the black range and the child has not already been diagnosed with cerebral palsy, the parent/legal guardian will be referred to a qualified examiner for a formal assessment to determine if this condition is present.

Reports from all specialists will be included in the subject's source documents. For further details regarding the ASQ-3 refer to the SPM.

An overview for the collection and review of data for the ASQ-3 is provided in [Figure 3](#).

Figure 3 ASQ-3, M-CHAT-R/F, and CBCL/1.5–5: Flow Chart of Data Collection and Review

ASQ-3 = Ages and Stages Questionnaire-3; BSID-III = Bayley Scales of Infant Development, third edition; CBCL/1.5–5 = Child Behavior Checklist for ages 1.5 to 5; HCP = health care provider; M-CHAT-R/F = Modified Checklist for Autism in Toddlers-Revised with Follow-Up; RCC-PI = research coordinating center-principal investigator.

1. A neurologic examination will also be conducted, if indicated.

6.2.5.2. Neurodevelopment

Neurodevelopment will be assessed by determining the proportions of infants diagnosed with developmental delays listed below at 9, 18, and 24 months of age, corrected for prematurity.

- Proportion of infants with an ASQ-3 score in the black zone for any domain
- Proportion of infants with an ASQ-3 score in the black zone for gross motor skills
- Proportion of infants with an ASQ-3 score in the black zone for fine motor skills
- Proportion of infants with an ASQ-3 score in the black zone for communication
- Proportion of infants with an ASQ-3 score in the black zone for problem-solving
- Proportion of infants with an ASQ-3 score in the black zone for personal-social skills
- Proportion of infants referred for developmental evaluation (using BSID-III)
- Proportion of infants with a BSID-III score >2 SDs below the mean score for cognitive impairment (<4)
- Proportion of infants with a BSID-III score >2 SDs below the mean score for the gross motor scale (<4)
- Proportion of infants with a BSID-III score >2 SDs below the mean score for the fine motor scale (<4)
- Proportion of infants with a BSID-III score >2 SDs below the mean score for the language scale (<70)
- Proportion of infants with a CBCL/1.5–5 above the 97th percentile for a subset of prespecified questions that relate to attention and hyperactivity problems
- Proportion of infants indicated as needing further evaluation after completion of the M-CHAT-R/F
- Proportion of infants referred for neurological evaluation to determine diagnosis of cerebral palsy

6.2.6. Overall Measure of Neurodevelopmental Impairment

- Proportion of infants with at least 1 of the following indicators of neurodevelopmental impairment:
 - Hearing impaired, uncorrected even with aids (at 24 months chronological age)
 - Blindness in 1 or both eyes, or sees light only (at 24 months chronological age)
 - Cerebral palsy (moderate defined as grade 2 or 3 and severe defined as grade 4 or 5 using the Gross Motor Functional Classification System [GMFCS]) (at 24 months corrected age)

- Cognitive impairment: BSID-III Cognitive Scale Score of >2 SDs below mean score (<4) (at 24 months corrected age)
- Motor impairment: BSID-III Motor Composite Scale Score of >2 SDs below mean score (<70) (at 24 months corrected age)
- Diagnosis of ASD, ADD, or ADHD

6.2.7. Adverse Events

The RCC-PI or RCC site staff will be responsible for detecting, documenting, and reporting events that meet the definition of an SAE. Nonserious AEs will not be tracked.

The outcomes for this study may represent a number of potential adverse drug experiences or events that include but may not be limited to the following:

- Reports of child hospitalizations (see Section [6.3](#))
- Reports of chronic health conditions in the child (see Section [6.2.2](#))
- Reports of congenital anomalies in the child (see Section [6.2.3](#))
- Reports of child death (see Section [6.2.4](#))
- Reports of developmental delays in the child (see Section [6.2.5.2](#))
- Reports of any other SAEs in the child (see Section [6.2.7.2](#))

6.2.7.1. Definition of an AE

Any untoward medical occurrence in a patient or clinical investigation subject, temporally associated with the use of a medicinal product, whether or not considered related to the medicinal product.

Note: An AE can therefore be any unfavorable and unintended sign (including an abnormal laboratory finding), symptom, or disease (new or exacerbated) temporally associated with the use of a medicinal product.

Events meeting the definition of an AE include:

- Exacerbation of a chronic or intermittent pre-existing condition including either an increase in frequency and/or intensity of the condition
- New conditions detected or diagnosed after study treatment administration even though it may have been present prior to the start of the study
- Signs, symptoms, or the clinical sequelae of a suspected interaction
- Signs, symptoms, or the clinical sequelae of a suspected overdose of either study treatment or a concomitant medication (overdose per se will not be reported as an AE/SAE) unless this is an intentional overdose taken with possible suicidal/self-harming intent. This should be reported regardless of sequelae.

Events that **do not** meet the definition of an AE include:

- Medical or surgical procedure (e.g., endoscopy, appendectomy); the condition that leads to the procedure is an AE
- Situations where an untoward medical occurrence did not occur (social and/or convenience admission to a hospital)
- Anticipated day-to-day fluctuations of pre-existing disease(s) or condition(s) present or detected at the start of the study that do not worsen
- The disease/disorder being studied, or expected progression, signs, or symptoms of the disease/disorder being studied, unless more severe than expected for the subject's condition

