1. INTRODUCTION

1.1. Background

Gestational age at birth is considered the most important predictor of a newborn's subsequent health and survival. Infants born too early and too small have a much greater risk of death and both short- and long-term disability than those born at term [Saigal, 2008]. Early morbidity due to prematurity includes respiratory distress syndrome, intraventricular hemorrhage, necrotizing enterocolitis, and sepsis. Late consequences of prematurity include chronic lung disease, cerebral palsy, sensory impairment, and cognitive deficits. An estimated 14.9 million babies were born prematurely in 2010, representing 11% of all live births worldwide [Blencowe, 2012]. Preterm birth rates ranged from approximately 5% in several European countries to 18% in some African countries. In 2013, nearly 450 000 preterm births, defined as childbirth occurring before 37 completed weeks' gestation, occurred in the United States [Martin, 2015]. These preterm infants had an infant mortality rate approximately 15 times the rate for full-term infants; the highest infant mortality rate occurs in infants born prior to 32 weeks' gestation [Matthews, 2010]. Although the risk for complications decreases with increasing gestational age, infants born just a few weeks before term carry an increased risk for developing medical complications, resulting in excessive mortality and morbidity rates during the birth hospitalization, as compared with the rates in full-term infants [Engle, 2007].

Prematurity directly influences the level of medical care, length of hospitalization, and associated costs; prematurity sequelae extend the need for continued medical care into childhood. Estimates for 2005 placed the annual economic cost in the United States at a minimum of 26.2 billion dollars or 51 600 dollars per infant born preterm; roughly two-thirds of this cost was for medical care [Behrman, 2007].

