Oxytocin plays a key role in term and preterm labor. It is a potent uterotonic whose role in the initiation and progression of human labor, both term and preterm, has been actively investigated for many years. Although preterm labor may well be a syndrome with various etiologies, oxytocin action on the uterus, in all likelihood, represents a common step in activation of the myometrium. Paracrine rather than endocrine mechanisms are thought to mediate this process, in which the effects of oxytocin are governed by tissue-specific oxytocin receptor expression, which leads to direct contractile effects in myometrium and prostaglandin formation in the decidua. Prostaglandins in turn mediate myometrial contractions and cervical ripening [Fuchs, 1982; Benedetto, 1990].

Retosiban (GSK221149) is a potent, competitive, and highly selective oxytocin receptor antagonist. Retosiban inhibits spontaneous and oxytocin-induced contractions in human myometrial tissue. Retosiban was being developed for the treatment of spontaneous preterm labor (SPTL) in women with intact membranes.

Phase III SPTL treatment studies were conducted to demonstrate the ability of retosiban to prolong pregnancy and improve neonatal health, as well as to describe the maternal, fetal, and neonatal safety profiles. The treatment studies were terminated due to limited

recruitment and the development program was subsequently terminated with no further in utero exposure planned.

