6.2. Safety

The focus will be on collecting the safety outcomes as defined in the objectives (e.g., hospitalization, death) and SAEs, including congenital anomalies. Nonserious AEs will not be tracked. All SAEs and safety outcomes will be followed until resolution, stabilization, or loss to follow-up.

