6.2.8. Laboratory and Other Safety Assessment Abnormalities Reported as SAEs

Any abnormal laboratory test results (hematology, clinical chemistry, or urinalysis) or other safety assessments (e.g., electrocardiograms, radiological scans, vital sign measurements), including those that worsen from Baseline, felt to be clinically significant in the medical and scientific judgment of the RCC-PI are to be recorded as SAEs. However, any clinically significant safety assessments that are associated with the underlying disease, unless judged by the RCC-PI to be more severe than expected for the subject's condition, are **not** to be reported as SAEs.

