6.2.14. Prompt Reporting of SAEs and Other Events to GSK/PPD

Serious AEs meeting predefined criteria will be reported promptly by the RCC-PI to GSK, as described in the following table, once the RCC-PI determines that the event meets the protocol definition for that event.

		Initial Reports		Follow-Up Information on a Previous Report	
Type of Event	Time Frame	Documents	Time Frame	Documents	
All SAEs	24 hours	“SAE” data collection tool	24 hours	Updated “SAE” data collection tool	
Cardiovascular or death event	Initial and follow-up reports to be completed within 1 week of when the cardiovascular event or death is reported	“CV events” and/or “death” data collection tool(s), if applicable	Initial and follow-up reports to be completed within 1 week of when the cardiovascular event or death is reported	Updated “CV events” and/or “death” data collection tool(s), if applicable	

CV = cardiovascular; SAE = serious adverse event.

The contact information for reporting SAEs is as follows:

Issue	North America Contract	Latin America Contact	Europe/Asia Contact
Serious Adverse Event Reporting	24-Hour Safety Hotline: PPD [REDACTED] Safety Fax: PPD [REDACTED]	24-Hour Safety Hotline: PPD [REDACTED] Safety Fax: PPD [REDACTED]	24-Hour Safety Hotline: PPD [REDACTED] Safety Fax: PPD [REDACTED]

The method of recording, evaluating, and following up of SAEs including procedures for completing and transmitting SAE reports to GSK are provided in the SPM. Procedures for poststudy SAEs are provided in the SPM.

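### An exclusion of the disease under study, undefined for the infant, can keep admissions for prematurity complications out of the SAE tables

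*Protocol*

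**What the plan says.** Protocol 6.2.7.1 lists what does not count as an adverse event, including: "The disease/disorder being studied, or expected progression, signs, or symptoms of the disease/disorder being studied, unless more severe than expected". Section 6.2.8 takes the same approach to laboratory and other assessments. It tells the investigator not to report as SAEs "any clinically significant safety assessments that are associated with the underlying disease, unless judged by the RCC-PI to be more severe than expected". Under 6.2.14, prompt reporting begins "once the RCC-PI determines that the event meets the protocol definition for that event".

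Other text points the other way. Section 6.2 states: "The focus will be on collecting the safety outcomes as defined in the objectives (e.g., hospitalization, death) and SAEs, including congenital anomalies". Section 6.2.7 opens with "The outcomes for this study may represent a number of potential adverse drug experiences or events" and then lists hospital admissions, anomalies, deaths, developmental delays and "Reports of chronic health conditions in the child". Section 6.2.7.1 itself counts conditions newly detected after treatment as AEs. Section 6.2.7.2 makes death, hospitalization, disability and congenital anomaly seriousness criteria. SAP 7.2.2.1 restates the SAE definition without any exclusion for a disease under study.

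**The concern.** The exclusion is standard wording for a trial in which the participant has the disease being treated. ARIOS infants receive no product, and no section names a disease under study for them. The drug's target was maternal: "Retosiban was being developed for the treatment of spontaneous preterm labor (SPTL) in women with intact membranes". A pediatrician applying the bullet to an infant would most naturally think of prematurity and its sequelae. Those sequelae are much of what the study follows: "Late consequences of prematurity include chronic lung disease, cerebral palsy, sensory impairment, and cognitive deficits".

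Several regional RCC-PIs make this call, with no criterion for what is expected. Two similar admissions for a prematurity complication could therefore be handled differently, one reported within 24 hours and counted in the SAE table, the other not reported. The study is meant to give assurance about early childhood safety, so its SAE count should not depend on each investigator's expectations.

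**Working it through.** The plan gives no figure that depends on the AE definition, so there is nothing to reproduce. The check compares the text and then sets a scale.

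**Which text governs?**

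1. Sections 6.2.7.1 (exclusion bullet) and 6.2.8 remove events that are not worse than expected. Section 6.2.8 names the RCC-PI as judge, and 6.2.14 makes reporting wait for the RCC-PI's decision.
2. Section 6.2.7 includes the outcomes as adverse events, but only as a possibility. The new-conditions bullet of 6.2.7.1 includes them more firmly.
3. Section 6.2.7.2 defines an SAE directly as an untoward occurrence meeting a seriousness criterion. Its note on elective admissions, however, works by saying that these are not AEs. This suggests that an event must first be an AE, so the exclusion could still apply.
4. No section ranks these texts or exempts Section 6.2 outcomes from the exclusion. The conflict is unresolved.

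**Where would an excluded event still be seen?**

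| Event type | Place outside the SAE tables |
|---|---|
| Chronic conditions | Tables 10.6/20.6 |
| Neurodevelopment and impairment | Tables 10.7–10.9/20.7–20.9 |
| Congenital anomalies | Tables 10.10/20.10; also an explicit SAE criterion |
| Deaths | Listing 44, disposition and milestone counts (SAP 6.2), own collection tool (Protocol 6.2.10) |
| Hospital admissions | Listing 46 only (SAP 7.2.6) |

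The gap is therefore mainly in admissions. One for a complication outside the fixed condition list of Protocol 6.2.2 would appear in no other by-group table. SAP 10.6.2 adds to this by treating missing safety data as no event.

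**Scale of one omission.** If an infant's only serious event is left out, the group's SAE percentage falls by 100/n points.

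- Table 20.5 (ARIOS Safety), using the enrolled numbers in the Amendment 02 justification in Protocol Appendix 1:
  - retosiban 100/49 = 2.0
  - atosiban 100/43 = 2.3
  - placebo 100/6 = 16.7
- Table 10.5 (Infant Safety), using the group sizes in Protocol 1.1.1 and assuming every participant was dosed and had one infant:
  - retosiban 10 + 50 = 60, so 100/60 = 1.7
  - atosiban 100/47 = 2.1
  - placebo 100/13 = 7.7

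The documents do not say how many events would be judged expected, so no total effect can be computed.

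**The case against.** The best defence is that the bullet does nothing here. If no infant disease is under study, it excludes nothing, and no section calls prematurity the disease studied. The morbidity endpoints are by definition newly diagnosed, which the same section counts as an AE. Section 6.2.7.2 also leans towards inclusion: complications during a hospital stay are AEs, and doubt about whether an admission occurred or was needed is resolved towards seriousness. SAE recording and evaluation are further described in the Study Procedures Manual, which is not among the documents reviewed and may settle the matter.

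Much of this stands. It shows an ambiguity rather than a clear rule against counting these events. It does not remove the problem, because nothing in the protocol tells an RCC-PI to read the bullet as empty, and 6.2.8 invites the opposite reading.

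Two stronger readings are tempting. A reader might infer that the study's endpoints are lost. They are not: under Confirmation of Parent-Reported Data (Protocol 6.2.1.1), morbidity and mortality endpoints need medical confirmation whatever their SAE status, and they have their own displays.

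A reader might also infer bias between arms, because what is expected depends on gestational age at birth, which treatment was meant to change. The documents do not show this. RCC-PIs are blinded (Protocol 5.3), and adjusted mean time to delivery in ZINN was 32.51 days with retosiban and 33.71 with atosiban. NEWBORN-1 shows a larger gap in time to delivery or treatment failure (18.9 against 11.1 days), but with only 10 and 13 women, and 6 placebo infants enrolled in ARIOS.

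**Conclusion.** The concern holds in a limited form. The exclusion is in force, is undefined for the infant and conflicts with neighbouring sections and with the SAP. It can keep serious prematurity complications, chiefly those leading to admission, out of 24-hour SAE reporting and out of Tables 10.5 and 20.5.

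The supported harm is under-counting and inconsistency between RCC-PIs, with no known direction between arms. It rests on an RCC-PI reading prematurity as the disease studied, which the text allows but does not require. The per-infant shifts show how sensitive small groups are, above all placebo; they do not estimate the error. The Table 10.5 shifts also depend on the assumed 60, 47 and 13 infants.

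**What to change.** Delete the bullet from 6.2.7.1 for ARIOS. Alternatively, state that neither it nor the matching sentence in 6.2.8 applies to Section 6.2 outcomes, or to complications of prematurity that meet a seriousness criterion in 6.2.7.2. If the bullet is deleted, 6.2.8 still needs aligning, since its exclusion would otherwise remain. The provisions on anticipated fluctuation of existing conditions and on elective admissions can stay, so a guard against over-reporting remains.

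Before database freeze and unblinding, compare the hospitalization and death records already required by Protocol 3.1 and Confirmation of Parent-Reported Data with the SAE dataset, and query any event that is missing.

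The cost is a short amendment or clarification to the RCC-PIs and one reconciliation, with no new data collection. SAE rates may come out somewhat higher.
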